# 14.3.12.4 Assessment of local tolerability

Assessment of local tolerability will be summarised by visit and treatment group.

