Trial design	The trial is a phase 3 randomised, double-blind, vehicle-controlled, parallel-group, multi-site trial in which adult subjects with moderate to severe CHE will be treated with delgocitinib cream 20 mg/g or cream vehicle for 16 weeks.
	The trial consists of a screening period, a treatment period, and a follow-up period.
	Screening period The screening period has a minimum duration of 1 week and a maximum duration of 4 weeks. At the screening visit, the subjects' eligibility to enter the trial will be checked, and wash-out of treatments listed as exclusion criteria will be initiated if applicable. In view of a 28-day wash out for some of these treatments, the screening period can be extended up to 31 days. The subjects will receive an eDiary device and training in completion of the eDiary.
	Treatment period At baseline (Day 1), the subjects' eligibility to enter the trial will be confirmed. If still eligible, the subjects will be randomised 2:1 to treatment with delgocitinib cream 20 mg/g or cream vehicle. The randomisation will be stratified by the baseline severity of CHE according to IGA-CHE (moderate and severe) and region (Europe and North America).
	The first application of IMP will occur at the trial site at baseline (Day 1). The subsequent IMP applications will be performed by the subjects at home twice daily for 16 weeks. During the treatment period, the subjects will be required to return to the trial site for the visits scheduled at Weeks 1, 2, 4, 8, 12, and 16. The last IMP application will occur at the subject's home before the subject attends the visit scheduled at Week 16.
	Follow-up period The subjects will attend a follow-up visit (performed via phone, but can be a site visit if needed) approximately 2 weeks after the last IMP application for assessment of safety. Eligible subjects who complete the treatment period (i.e. who do not permanently discontinue IMP prior to Week 16) will be invited to

Page 20 of 157

participate in an open-label LTE trial (LP0133-1403, conducted under a separate protocol). Subjects who continue in the LTE trial will not be required to complete the follow-up period, as collection of safety data and safety surveillance will continue in the LTE trial.

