- 15) Completion of HESD in the eDiary will be initiated at least 1 week prior to baseline (Day 1), but preferably from the date the subjects receive the eDiary. Compliance with the eDiary completion will be reviewed by the trial site staff throughout the trial. Subjects who discontinue IMP but remain in the trial will continue completing HESD in the eDiary until the primary endpoint visit at Week 16.
- 16) Includes Itch PGI-S, Pain PGI-S, and HESD PGI-S.
- 17) Includes Itch PGI-C, Pain PGI-C, and HESD PGI-C.
- 18) Subject assessment of local tolerability will be evaluated weekly by the subject in the eDiary from Day 7 onwards up to end of treatment/early termination.

- 19) Subjects do not have to be fasting for safety laboratory samples.
- 20) For women of childbearing potential (as defined in inclusion criterion no. 8, Section 8.2).
- 21) It will be at the investigator's discretion to decide whether a urine sample should be sent to the central laboratory for further analysis.
- 22) Only applicable if the investigator suspects a local skin reaction related to IMP application based on the initial inspection of the subject's hands and the subject's assessment of local tolerability (Section 11.5.5). The investigator will score the local skin reaction (Section 11.5.5) and perform an IMP patch test with the subject's (blinded) IMP to classify the aetiology of the reaction (see Section 11.5.5.1).
- 23) The PK blood samples should be taken 2-6 hours post application of IMP.
- 24) Photography will require additional informed consent with the possibility to choose for which purpose (scientific and/or commercial) the photographs can be used. If deemed necessary (e.g. in case of poor quality), photographs can be retaken at the next visit or at an unscheduled visit.
- 25) Subjects who continue to the LTE trial must bring the eDiary to the Week 16 visit so the trial site staff can set up the eDiary for the LTE trial. Daily completion of the eDiary will continue in the LTE trial.
- 26) Not applicable at the early termination visit if the subject does not withdraw from the trial, as subjects who discontinue IMP but remain in the trial will continue completing the eDiary until the primary endpoint visit at Week 16.

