#### 9.2 Administration of IMP

The IMP (delgocitinib cream 20 mg/g or cream vehicle) will be applied as a topical application twice daily for 16 weeks. The applications will be performed approximately 12 hours apart. Instructions for use will be provided to subjects.

The IMP will be applied to clean, dry hands, fingers, fingertips, and wrists in a thin layer covering the affected areas. The amount of IMP to be used depends on the size of the affected area and the size of the hands, fingers, fingertips, and wrists. 1 tube of 15 g delgocitinib cream is considered sufficient for treatment of the whole surface of hands, fingers, fingertips, and wrists twice daily for 1 week; however, a few subjects may need more (based on experience from the LP0133-1273 trial), which will be allowed at the discretion of the investigator.

Page 53 of 157

The first application of IMP will occur at the trial site. Prior to the first IMP application, the subject will be instructed on how much cream to apply and which area(s) to treat.

Only the affected area(s) on the hand(s), finger(s), fingertip(s), and wrist(s) will be treated. If new CHE lesions occur on initially untreated area(s) of the hand(s), finger(s), fingertip(s), and wrist(s), these new lesions will be treated with IMP as well. The subjects will be advised to contact the investigator before initiating treatment of new lesions. The IMP application on initially affected areas and new lesions will continue until Week 16 regardless of clearance status. The last IMP application will occur at the subject's home before the subject attends the visit scheduled at Week 16.

At the scheduled trial visits, investigator assessments of efficacy should preferably be done at least 2 hours after application of IMP and/or emollient. Recommendations for bathing, washing, and hand sanitising in relation to IMP application are provided in Section 9.6.

The IMP will be dispensed by the investigational staff at the visits scheduled in Section 4. Returned, opened IMP tubes will be weighed at the trial site to determine the amount of IMP used (see Section 9.8.3).

The investigator will use clinical judgement to treat any symptoms connected with an overdose.

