# 11.5.5 Assessment of local tolerability

Subjects and investigators will each provide an assessment of local tolerability according to the schedule of trial procedures (Section 4).

The subject will complete a weekly assessment of stinging/burning in connection with the IMP applications in the eDiary from Day 7 onwards. The subject will be asked to retrospectively assess the worst stinging/burning in connection with the IMP application during the last week. In addition, the subject will be asked by the investigator at the end-of-treatment/early termination visit to assess the local tolerability during the last week (see Section 4). The assessment will be done using the 4-point scale shown in Panel 15.

Panel 15: Subject assessment of local tolerability after IMP application

Grade (severity)	Stinging/burning
0 (none)	No stinging or burning.
1 (mild)	Slight warm, tingling sensation, not really bothersome.
2 (moderate)	Definitive warm, tingling sensation, that is somewhat bothersome.
3 (severe)	Hot, tingling/stinging sensation that has caused definite discomfort.

**Abbreviation:** IMP = investigational medicinal product.

The investigator will assess whether he/she suspects a local skin reaction related to application of the IMP. If the investigator suspects a local skin reaction related to application of the IMP, the skin reaction will be scored according to the Berger and Bowman scales in

Page 79 of 157

Panel 16. The scoring should only assess skin signs suspected to be related to application of the IMP and not signs or symptoms related to the subject's CHE.

Following scoring according to the Berger and Bowman scales, an IMP patch test will be performed to confirm a possible diagnosis of allergic contact dermatitis caused by the IMP, see procedure described in Section 11.5.5.1. The aetiology of the local skin reaction will be captured in the eCRF and the final diagnosis will be captured as an AE.

The subject's assessment of local tolerability may be reported as an AE at the discretion of the investigator, even if the investigator does not suspect a local skin reaction related to application of IMP (reporting of e.g. pain or stinging/burning by the subject).

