# 14.3.14 General principles

Significance tests, for binary and continuous endpoints, will be one-sided using the 2.5% significance level. The Gray's test, used for time-to-event endpoints, will be two-sided using a 5% significance level. All confidence intervals will be presented with 95% degree of confidence, unless otherwise specified.

An observed-cases approach will be used for tabulations of data by visit (that is, involving only those subjects who attended each specific visit).

Page 129 of 157

Categorical data will be summarised using the number and percentage of subjects in each category. Continuous data will be summarised using the mean, median, SD, 1st quartile, 3rd quartile, minimum, and maximum values.

Baseline measurements will be defined as the latest available observation at or prior to the date of randomisation.

All the analyses specified in the protocol will be reviewed in relation to the blinded data actually obtained, and the statistical analysis plan will be finalised before breaking the randomisation code.

Any changes from the statistical analyses planned in this clinical trial protocol will be described and justified in a protocol amendment, the statistical analysis plan, and/or in the CTR, dependent on the type of change.

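### Local tolerability is summarised only by visit, so 10 of the 16 weekly stinging/burning ratings have no stated place and no table gives each subject's worst grade

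*Combined protocol and SAP*

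**What the plan says.** Section 11.5.5 describes two assessments of local tolerability.

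- **Subject.** "The subject will complete a weekly assessment of stinging/burning in connection with the IMP applications in the eDiary from Day 7 onwards" Each entry looks back one week: "The subject will be asked to retrospectively assess the worst stinging/burning in connection with the IMP application during the last week". The scale runs from 0 (none) to 3 (severe). Panel 2, footnote 18, says that the rating "will be evaluated weekly by the subject in the eDiary from Day 7 onwards up to end of treatment/early termination". The subject also gives one rating, covering the last week, at the end-of-treatment or early termination visit.
- **Investigator.** Panel 2 schedules this assessment at Weeks 1, 2, 4, 8, 12 and 16 and at early termination. If a reaction to the cream is suspected, it is scored on the Berger and Bowman scales and followed by a patch test with the subject's own product.

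The analysis of both is one sentence in Section 14.3.12.4: "Assessment of local tolerability will be summarised by visit and treatment group". Section 14.3.14 adds that "An observed-cases approach will be used for tabulations of data by visit", and explains that such tables include only subjects who attended the visit in question. The documents contain no rule that assigns diary weeks to visits, no summary by diary week, and no summary of a subject's worst grade over the treatment period.

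**The concern.** The subject's rating and the table that reports it run on different clocks: one is weekly, the other follows a visit schedule that thins to every four weeks after Week 4. Because each rating covers only the preceding week, the rating from a visit week cannot stand in for the weeks skipped.

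A second problem does not depend on how visits are defined. For a topical cream, one natural safety question is how many subjects in each arm had moderate or severe stinging/burning at any time. A series of columns by time point shows the share affected at each point, but does not count each subject once at his or her worst. The protocol itself lists burning and stinging among the possible local reactions (Section 5.5) and makes the comparison of safety with vehicle a secondary objective (Panel 4). At stake is how completely a safety measure that is already being collected gets reported.

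**Working it through.** The plan states no figure on this point, so there is none to reproduce. The check is a count.

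**Inputs**

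- Treatment length: the product "will be applied as a topical application twice daily for 16 weeks" (Section 9.2).
- Diary ratings: weekly from Day 7 (Section 11.5.5; Panel 2, footnote 18). Over 16 weeks these fall on Days 7, 14, ..., 112, and 112 / 7 = 16 ratings.
- On-treatment visits: subjects "return to the trial site for the visits scheduled at Weeks 1, 2, 4, 8, 12, and 16" (synopsis), which is 6 visits.

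**Step 1: ratings without a visit.** Credit each visit with the diary rating of the same week. The plan states no such matching rule, so this is an assumption.

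- With a visit: 6 of 16 = 37.5%.
- Without a visit: 16 − 6 = 10, and 10 / 16 = 62.5%. These are Weeks 3, 5, 6, 7, 9, 10, 11, 13, 14 and 15.

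**Step 2: does the end of treatment change the count?** The Week 16 visit has a window of ±3 days around Day 113. Letting the last diary day run from Day 109 to Day 116:

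- Last diary day before Day 112: 15 ratings, with the same 10 unmatched (10 / 15 = 66.7%).
- Last diary day on or after Day 112: 16 ratings, 10 unmatched.
- If the Week 16 column uses the rating given at the visit instead of the last diary entry (the text does not say which): 10 + 1 = 11 unmatched, and 11 / 16 = 68.75%.

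**Step 3: which episodes would not show.** A run of k symptomatic weeks can start in 16 − k + 1 positions. The table misses it if no week of the run is a visit week. As an illustration, treat all positions as equally likely:

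| Length of run | Positions | Missed | Share missed |
|---|---|---|---|
| 1 week | 16 | 10 | 62.5% |
| 2 weeks | 15 | 6 | 40.0% |
| 3 weeks | 14 | 3 | 21.4% |
| 4 weeks | 13 | 0 | 0% |

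The longest gap between visit weeks is three weeks (for example Weeks 5 to 7), so an episode of four weeks or more always reaches at least one column. Weeks 1 and 2 are both visit weeks, so reactions at the start of treatment are shown.

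**Step 4: why columns do not give the share ever affected.** Let p_t be the share at grade 2 or higher in column t, for a fixed group of subjects, and let P be the share at grade 2 or higher in any column. Then

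max(p_t) ≤ P ≤ min(1, sum of p_t).

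The lower limit applies when everyone affected at any time point is also affected at the peak one; the upper limit applies when different subjects are affected each time. The columns alone cannot tell these apart, whether there are 6 or 16 of them. With observed cases the group also changes from column to column, which loosens the limits further.

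**Step 5: is a worst-grade summary planned elsewhere?**

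- Section 11.5.5 records a highest score in the eCRF, but that is across treatment areas at one visit, not over time.
- Section 14.3.12.1 counts subjects with at least one adverse event, and shows severity. Under Sections 11.5.5 and 13.2, a subject's rating enters those tables only if the investigator judges it relevant, unless a skin reaction to the cream is suspected, in which case the final diagnosis must be recorded.

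Neither supplies the worst diary grade per subject.

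**The case against.** The case for leaving the text alone has four parts.

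1. **The by-visit cut has a proper use.** Section 14.3.12.4 covers both assessments in Section 11.5.5, and the investigator's is made at exactly those visits. This stands, and it means that the by-visit table must not be removed. A reader might infer that the diary item is the trial's only structured measure of local tolerability. The investigator's scheduled assessment, with Berger and Bowman scoring and a graded patch test when a reaction is suspected, shows that it is not.
2. **Adverse events give a count of subjects ever affected.** Section 13.2 has local tolerability queried specifically, and Section 14.3.12.1 reports the number and percentage of subjects with at least one event, including events between visits. A reader might infer that the adverse event tables do nothing here; that goes too far. The coverage is real but partial, because stinging/burning without a suspected skin reaction is left to the investigator's judgement.
3. **This is table-shell detail.** Section 14.3.14 says that the statistical analysis plan will be finalised before unblinding, so a weekly or worst-grade table could be added there. If visits were read as diary weeks, the count of 10 would disappear. Both statements are fair. The present text contains no such rule, however, and defines by-visit tables through attendance. The missing worst grade remains on either reading.
4. **The consequence is limited.** All ratings are collected, early weeks are shown, both arms are tabulated alike, and no test of tolerability is planned. This stands and sets the weight of the point.

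**Conclusion.** The point holds as a minor gap in safety reporting. Read literally, Sections 14.3.12.4 and 14.3.14 leave 10 of 16 weekly subject ratings (62.5%) untabulated for a subject who completes treatment, or 11 of 16 if the Week 16 column uses the visit rating. This rests on reading visits as Section 14.3.14 defines them and on matching each visit to the diary rating of the same week. On any reading, no planned table shows each subject's worst grade over treatment.

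Two stronger conclusions are tempting but not supported. A reader might infer that the comparison between arms is biased; nothing in the documents shows this, since both arms are rated and summarised in the same way. A reader might also want to state how many affected subjects would be overlooked. The documents give no weekly rate of stinging/burning and no correlation between weeks, so Step 4 gives only limits and Step 3 only an illustration. Efficacy, power and type I error are untouched.

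**What to change.** In Section 14.3.12.4, or in the statistical analysis plan before unblinding, separate the two assessments.

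- **Investigator's assessment:** keep the summary by visit and arm.
- **Subject's rating, main table:** worst grade (0 to 3) per subject over all weekly eDiary ratings plus the end-of-treatment or early termination rating, by treatment group, with the number and percentage of subjects at grade 2 or higher in any week.
- **Subject's rating, supporting table:** grades by diary week and treatment group, Weeks 1 to 16. State whether the Week 16 row uses the last diary entry or the rating given at the visit.

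The cost is a few lines of text and one or two extra descriptive tables. No new data are needed.

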# 14.3.13 Interim analysis

No interim analysis is planned.

# 14.3.14 General principles

Significance tests, for binary and continuous endpoints, will be one-sided using the 2.5% significance level. The Gray's test, used for time-to-event endpoints, will be two-sided using a 5% significance level. All confidence intervals will be presented with 95% degree of confidence, unless otherwise specified.

An observed-cases approach will be used for tabulations of data by visit (that is, involving only those subjects who attended each specific visit).

Page 129 of 157

Categorical data will be summarised using the number and percentage of subjects in each category. Continuous data will be summarised using the mean, median, SD, 1st quartile, 3rd quartile, minimum, and maximum values.

Baseline measurements will be defined as the latest available observation at or prior to the date of randomisation.

All the analyses specified in the protocol will be reviewed in relation to the blinded data actually obtained, and the statistical analysis plan will be finalised before breaking the randomisation code.

Any changes from the statistical analyses planned in this clinical trial protocol will be described and justified in a protocol amendment, the statistical analysis plan, and/or in the CTR, dependent on the type of change.

# 14.3.15 Handling of missing values

The methods for handling of missing values in the different analyses are described in Section 14.3.6.

Page 130 of 157

# **Appendix 1: Definitions of adverse events and serious adverse events**

## Adverse event definition

An AE is defined as any untoward medical occurrence in a patient or clinical investigation subject administered a pharmaceutical product and which does not necessarily have a causal relationship with this treatment. An AE can therefore be any unfavourable and unintended sign (including an abnormal laboratory finding), symptom, or disease temporally associated with the use of a medicinal (investigational) product, whether or not related to the medicinal (investigational) product (44).

#### This definition includes:

- Accidental injuries.
- Events related to trial procedures.
- Reasons for any unfavourable and unplanned change in medication (drug and/or dose).
- Clinically significant worsening of pre-existing conditions.
- Reasons for admission to hospital or surgical procedures\*.
- AEs commonly observed and AEs anticipated based on the pharmacological effect of the IMP
- Any laboratory abnormality assessed as clinically significant by the investigator (see Section 11.5.4.2).

## Serious adverse event definition

An SAE is any untoward medical occurrence that:

- Results in death.
- Is life-threatening at risk of death at the time of the SAE (not an event that hypothetically might have caused death if more severe).
- Requires in-patient hospitalisation or prolongation of existing hospitalisation\*.
- Results in persistent or significant disability or incapacity.
- Is a congenital anomaly or birth defect.

Page 137 of 157

• Is a medically important condition. Events that may not be immediately life-threatening or result in death or hospitalisation but may jeopardise the subject or may require intervention to prevent one of the other outcomes listed in the definition above. Examples are intensive treatment in an emergency room or at home for allergic bronchospasm, blood dyscrasias, and convulsions that do not result in hospitalisation, development of drug dependency, or drug abuse.

- \*Hospitalisation for procedures or treatments planned prior to the subject consented to trial participation does not constitute an AE and should therefore not be reported as an AE or SAE.
- \*Hospitalisation for elective treatment of a pre-existing condition which did not worsen from the subject consented to trial participation is not considered an AE and should therefore not be reported as an AE or SAE, even if not planned before consent to trial participation.
- \*Hospitalisation for routine scheduled treatment or monitoring of the studied indication not associated with any aggravation of the condition does not constitute an AE and should therefore not be reported as an AE or SAE.
- \*Hospitalisation for administrative, trial-related, or social purpose does not constitute an AE and should therefore not be reported as an AE or SAE.
- \*Complications that occur during hospitalisation are (S)AEs. If a complication prolongs hospitalisation, the event is an SAE.
- \*When in doubt as to whether hospitalisation occurred or was necessary, the AE should be considered serious.

Additionally, all malignancies, incl. skin malignancies, should be reported as SAEs.

